6.4. Subgroup Analyses

Not applicable due to the small sample size and exploratory nature of the study.

6.5. Baseline and Other Summaries and Analyses

6.5.1. Baseline Summaries

The following demographic and baseline characteristics will be summarized for all patients in the AT population.

- Age, race, ethnicity, height (cm), weight (kg), and body mass index (kg/m²).
- PSA (ng/mL) and Gleason scores.
 - From the medical history prostate cancer CRF page.
- Primary diagnosis.
 - Continuous summary of time from primary diagnosis to study enrollment (in years).
- ECOG status.
 - Tabulations with n (%) for the different categories.
- Brief Pain Inventory (Short Form).
 - Yes/No categories will be tabulated with n (%).
 - Categories scaled from 0 to 10, or from 0% to 100%, will be summarized as a continuous measure using descriptive statistics.
- Medical history.
 - Derived from the medical history non-prostate cancer CRF page.

Listings will be provided for these parameters.

6.5.2. Protocol Deviations

Protocol deviations will be compiled prior to database closure and will be summarized by category (n(%)) for the AT population. Categories will be assigned by the study clinician.

6.5.3. Study Conduct and Patient Disposition

Summaries will include the number and percentage of patients in AT population.

The number and percentage of patients who discontinue study drug and the reasons for discontinuation will be summarized for all patients in the AT population. Likewise the number and percentage of patients who discontinue the study itself will be summarized for all patients in the AT population.

6.5.4. Prior and Current Therapies

Prior therapies and current therapies will be summarized separately for patients in the AT population:

- Radiotherapy for prostate cancer.
- Surgical procedures for prostate cancer.

6.5.5. Study Drug Exposure and Treatment Compliance

[figure not shown]
Study Drug Exposure

Summary statistics will be provided for all patients in the AT population for:

- Treatment duration (months): For each patient, treatment duration is defined as (date of last dose date of first dose +1)/30.4375. Treatment duration will be summarized both as a continuous measure and a categorical measure (<3 months, 3 to <6 months, 6 to <12 months, 12 to <24 months, 24 to <36 months, and ≥36 months).
- Cumulative dose (mg): For each patient, the cumulative dose is calculated based on the Study Drug Dosing CRF page. The daily total dose (mg) will be summed across the study.
- Average daily dose (mg/day): The average daily dose is defined as the cumulative dose divided by the dose exposure.
 - Dose exposure (days) is defined as the total number of actual days on study drug during the treatment period.

Treatment Compliance

• Percent overall compliance will be summarized both as a continuous measure and a categorical measure (<80%, ≥80%).

Percent overall compliance rate will be defined as the number of capsules taken during the study divided by the expected number of capsules, multiplied by 100%, as specified in section 10.5 of the protocol. Capsules not returned will be assumed to have been taken, as per section 6.3 of the protocol. The number of returned capsules is obtained from the Study Drug Accountability CRF page. A patient's expected number of capsules, if no dose modifications, will be calculated as $[4 \times (date of last dose - date of first dose of study drug + 1)]$. Adjustments to the expected number of capsules are made if dose adjustments occurred:

- If a dose reduction to 120mg, then subtract one capsule from the above formula for every day on the 120mg dose.
- If a dose reduction to 80mg, then subtract two capsules from the above formula for every day on the 80mg dose.
- If a dose interruption, then subtract the appropriate number of capsules (4 or 3 or 2) from the above formula for every day of interruption.

Dose Interruptions and Reductions

Dose modifications include dose interruptions and/or reductions. A dose interruption will include a missing or a zero dose on the dosing page. A dose reduction is any dose that is lower than the previous dose. Dosage of enzalutamide may be reduced to either 120 mg/day, or 80 mg/day.

[figure not shown]
- Patients with at least 1 dose modification (interruption or reduction) and the reason for the dose modifications will be tabulated.
- Patients with at least 1 dose interruption will be tabulated.
- Patients with at least 1 dose reduction will be tabulated.

A data listing will be provided to present dose administration, modifications, and the derived compliance variables.

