Duration of Treatment: Patients will receive enzalutamide treatment daily as defined in Methods. After NaF-3 is completed, another therapy may be added to enzalutamide as long as it is not another androgen receptor inhibitor, cytotoxic chemotherapy, or an investigational drug. Patients may continue to receive treatment with enzalutamide for as long as the investigator considers it beneficial.

Statistical Methods:

The study endpoints are as follows:

Primary:

- The proportion of patients with at least 1 responding bone lesion (defined as a lesion with a total standardized uptake value [$\text{SUV}_{\text{total}}$] less than that at baseline) on the third ¹⁸F-NaF PET/CT [NaF-3] scan performed for each patient. This assessment will be triggered by disease progression (as defined in Methods) or at 2 years without progression after treatment initiation.

Secondary:

- The heterogeneity of response across all bone lesions as determined by the global heterogeneity of NaF standardized uptake value ($\text{SUV}_{\text{hetero}}$) when the primary endpoint is determined for each patient

CCI

CCI

The primary efficacy endpoint analysis will include patients who undergo at least NaF-1 and NaF-3 ¹⁸F-NaF PET/CT imaging. Definitions of the NaF uptake measures are as follows:

- SUV_{total} Total NaF uptake, which represents the tumor burden across all (global) bone lesions or in individual lesions
- SUV_{hetero} Heterogeneity of NaF uptake, which represents heterogeneity of lesion activity
- SUV_{mean} Mean NaF uptake, which represents the average activity of all lesions
- SUV_{max} Maximum NaF uptake, which represents the activity of the most aggressive lesion
- N Total number of lesions, which represents a numerical sum of all lesions
- VF Volume fraction, which represents the fraction of skeletal involvement

The global SUV_{hetero} score is a measure of the heterogeneity of tumor activity across all bone lesions and is defined as follows, where g = global, l = lesion, N = number of bone lesions.

$$gSUV_{hetero} = \frac{\sum_{i=1}^N (lSUV_{mean}^i - gSUV_{mean})^2}{N}$$

In other words, the global SUV_{hetero} score is the sum of the squares of the differences between the SUV_{mean} for each bone lesion and the global SUV_{mean} , divided by the number of lesions. Thus, a higher global SUV_{hetero} score reflects more heterogeneity in bone lesion activity.

CCI

Circulating tumor cells:

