5.2.1 Visit Windows

At each specified study visit, procedures will be performed according to the schedule of activities ([Appendix 2](#)).

A study visit may be scheduled on any day within a specified study week. For any given day within the study week, the visit window is ± 7 days (ie, 7 days before or after the given day) except for weeks 5 and 13 (± 3 days). There is no visit window for week 1, day 1.

Study drug supplies must be taken into account when scheduling visits during windows. Procedures for a given visit may be split across the window to allow for drug resupply and completion of study procedures.

5.2.2 Week 1, Day 1

Day 1 procedures are listed in Table 2. Study site personnel should ensure that a medical monitor-approved Enrollment Authorization Form is in the patient’s file before proceeding with day 1 procedures.

Table 2: Week 1, Day 1 Procedures

Activity / Assessment	Comment
General Activities	
Complete physical examination	May skip if performed within prior 3 days. Measure vital signs (temperature, blood pressure, and heart rate), and weight. ECOG performance status (Table 13). Assess systems per standard of care at the study site.
Adverse events review	Record adverse events that occurred during screening on the medical history case report form and in the patient’s source documents. Do not record such events on the adverse event case report form.
Concomitant medications review	Record any new medications or changes in ongoing medications.
Enzalutamide dispensing	Provide the patient with a 12-week supply. Provide instructions for dosing, storage, and return of all bottles (used and unused) of study drug at future visits.
Local Laboratory Evaluations	
Serum chemistry, hematology	May skip if performed within prior 3 days. Refer to analytes listed in Table 12.
PSA	
Central Laboratory/Imaging Evaluations	
Circulating tumor cells	Collect blood sample predose and process per laboratory manual instructions.
¹⁸ F-NaF PET/CT imaging (NaF-1)	Perform predose. Must perform within 7 days before first dose of enzalutamide. Perform a second baseline scan on up to 5 patients at each study site to assess reproducibility.

5.2.3 Week 5

The visit window is ±3 days. Drug supply must be taken into account if a window is used to schedule the next visit.

Week 5 procedures are listed in Table 3.

Table 3: Week 5 Procedures

Activity / Assessment	Comment
General Activities	

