5.2.5 Week 21 and Repeating Every 8 Weeks

Visits repeat every 8 weeks (\pm 7 days) until criteria are met for permanent treatment discontinuation (Section 5.3). Drug supply must be taken into account if a window is used to schedule the next visit. Assessments are performed at every visit or every other visit as noted.

Week 21 procedures are listed in Table 5.

Table 5: Week 21 and Repeating Every 8 Weeks Procedures

Activity / Assessment / Timing	Comment
General Activities	
Brief physical examination → Perform every 16 weeks (± 7 days)	Measure vital signs (temperature, blood pressure, and heart rate), weight, and ECOG performance status (Table 13). Perform symptom-directed examination and investigate any new abnormalities.
Adverse events review	Record any new or ongoing adverse events.
Concomitant medications review	Record any new medications or changes in ongoing medications.
Enzalutamide dispensing (if applicable)	Provide the patient with an 8-week supply. Provide instructions for dosing, storage, and return of all bottles (used and unused) of study drug at future visits.
Study drug accountability	Record study drug returned and remind patient to return all bottles (used and unused) at each future visit.
Local Laboratory Evaluations	
Serum chemistry, hematology → Perform every 16 weeks (± 7 days)	Refer to analytes listed in Table 12.
PSA	

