6.3 Treatment Compliance

Accountability for the study drug capsules (enzalutamide) will be performed to document compliance with the dosing regimens. Patients will be asked to bring all used and unused study drug bottles to study visits. Study site personnel must make reasonable efforts to obtain used and unused study drug bottles from patients who do not routinely return them at study site visits.

Unreturned capsules will be considered to have been taken.

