2. INTRODUCTION & STUDY DESIGN

This SAP provides detailed methodology for summary and statistical analyses of the data collected in study MDV3100-18. This document may modify the plans outlined in the protocol; however, any major modifications of the primary endpoint definition or its analysis will also be reflected in a protocol amendment. Any deviations from this analysis plan will be described in the Clinical Study Report (CSR).

MDV3100-18 is a phase 2, open-label, single-arm trial of enzalutamide in adult male patients who are chemotherapy-naïve, and who have bone-metastatic castration-resistant prostate cancer.

In this study, approximately 20 adult male patients (age ≥ 18 years) will be enrolled across 3 sites in the United States. The primary objective is to evaluate F-NaF PET/CT imaging as a method for assessing treatment response in metastatic bone lesions either at time of disease progression, or after 2 years of treatment, whichever comes first.

The primary analysis will include all data up to a data cutoff date which will be determined when all patients have progressed or have otherwise been followed for two year or are no longer being followed due to withdrawal of consent, lost to follow-up, or death. All summaries and analyses will include all data pertaining to visits/assessments (both planned and unplanned) performed up to and including the data cutoff date.

[figure not shown]

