3.4. Baseline Variables

The date of first dose (start date) of study treatment is the earliest date of non-zero dosing of the study drug. The date of last dose of study treatment is the latest date of non-zero dosing of the study drug.

No windowing will be applied when defining baseline. Any deviations from the protocol specified window will be documented as protocol deviations. For efficacy analyses and baseline characteristics associated with tumor assessments, the last assessment prior to the date and time of first study drug will serve as the baseline assessment.

For safety, the last assessment performed on or prior to date of the first dose of study treatment will serve as the baseline assessment. If there are no observations meeting these criteria, then baseline is considered missing.

Post-baseline value is defined as a measurement taken after the first administration of study drug. Change from baseline is defined as (post baseline value – baseline value). Percent change from baseline is defined as [(post baseline value – baseline value)/(baseline value)] multiplied by 100%. Both date and time of study drug administration and measurement will be considered when calculating baseline value. If time is not available, then date only will be used.

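### SAP 6.5.5 counts every unreturned capsule as taken but ends expected capsules at the last dose, so reported compliance can exceed 100% or hide under-dosing (minor, descriptive table only)

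*SAP*

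**What the plan says.** **Numerator.** Protocol 6.3 sets the rule, "Unreturned capsules will be considered to have been taken", and SAP 6.5.5 adopts it: "Capsules not returned will be assumed to have been taken, as per section 6.3 of the protocol". Capsules taken are therefore capsules dispensed minus capsules returned.

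**Denominator.** SAP 6.5.5 takes expected capsules as four times ("date of last dose - date of first dose of study drug + 1"), reduced for days on a lower dose or off drug. SAP 3.4 fixes the end point: "The date of last dose of study treatment is the latest date of non-zero dosing of the study drug".

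**Supply.** On day 1 the protocol (Table 2) says "Provide the patient with a 12-week supply". At week 13 if treatment continues, and every 8 weeks from week 21 (Tables 4 and 5), it says "Provide the patient with an 8-week supply".

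**Cutoff.** SAP section 2 says "The primary analysis will include all data up to a data cutoff date which will be determined when all patients have progressed", have been followed for two years, or have left follow-up. The protocol synopsis adds "Patients may continue to receive treatment with enzalutamide for as long as the investigator considers it beneficial", so some men may still be on drug at that date.

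**Reporting.** Compliance is summarised as a continuous variable and in two categories, <80% and ≥80%. There is no cap, no rule for unaccounted bottles, no rule for supply in hand at the cutoff and no separate treatment of values above 100%.

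**The concern.** The two halves of the ratio cover different periods. The numerator includes every capsule handed out and not brought back. The denominator covers only the days up to the last dose. Unused capsules that are not returned inflate the ratio, and the effect is largest when exposure is short because the denominator is small.

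The same rule can also fail in the opposite direction. A man who skips doses and returns nothing is credited with the whole supply. His value looks normal, so neither the median nor a glance at the range reveals it.

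The documents foresee both situations. Protocol 6.3 mentions patients who do not routinely return bottles, Protocol 5.4 and 5.5 provide for patients who refuse visits or are lost, and men with a PSA rise may leave at week 13. At stake is a misleading compliance mean, SD and category count in a study of about 20 men.

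**Working it through.** The documents give no compliance figure to reproduce, so the check applies the SAP formula to the protocol's dispensing schedule.

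**Inputs**
- Day 1 supply (Protocol Table 2): 12 × 7 × 4 = 336 capsules.
- Each later supply (Protocol Tables 4 and 5): 8 × 7 × 4 = 224 capsules, on days 85, 141, 197, … 701, 757 (visit days from Protocol Appendix 2 and SAP Appendix 3).
- Expected capsules for a last dose on day T (SAP 6.5.5): 4 × T.
- Number of patients: about 20 (Protocol 10.6).

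**Assumptions:** on-schedule visits, exact supplies (bottle size is not stated), 160 mg/day throughout, nothing returned.

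**Ceiling** = 100 × [336 + 224 × (later dispensing visits up to day T)] / (4 × T)

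Check: T = 84 gives 336/336 = 100%, as it should.

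The last column is the shift in a 20-patient mean from one such patient whose true value is 100%, that is (ceiling − 100)/20.

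| Last dose | Dispensed | Expected | Ceiling | Shift in mean (points) |
|---|---|---|---|---|
| Day 29 | 336 | 116 | 289.7% | +9.5 |
| Day 85, just dispensed | 336 + 224 = 560 | 340 | 164.7% | +3.2 |
| Day 365, just dispensed | 336 + 6 × 224 = 1680 | 1460 | 115.1% | +0.8 |
| Day 701, just dispensed | 336 + 12 × 224 = 3024 | 2804 | 107.8% | +0.4 |
| Day 730 | 3024 | 2920 | 103.6% | +0.2 |
| Day 756 | 3024 | 3024 | 100.0% | 0 |

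From week 13 on, the excess is at most 224 − 4 = 220 capsules, so it shrinks as a percentage with time on drug. Over last-dose days 701 to 756 the ceiling runs from 100.0% to 107.8% and averages 103.8%.

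**Effect on a group summary (hypothetical).** Take 18 men at an assumed 98%, one at 289.7% and one at 164.7%. The mean is (18 × 98 + 289.7 + 164.7)/20 = 110.9%, with SD 44.6 and median 98.0%.

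**Masking.** A man takes 60% of his capsules to day 84, about 0.6 × 336 = 202, and returns none. He is scored 336/336 = 100% and placed in ≥80%.

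**Check of the repair.** Drop the open interval, both its capsules and its days, for a fully compliant man seen on a dispensing day:
- Day 85: 336/(4 × 84) = 100%, instead of 164.7%.
- Day 141: 560/(4 × 140) = 100%, instead of 139.0%.
- Day 309: 1232/(4 × 308) = 100%, instead of 117.8%.
- Day 701: 2800/(4 × 700) = 100%, instead of 107.8%.

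**The case against.** The best defence is that the plan limits the problem at several points.

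- **Recovery of drug.** Protocol 6.3 requires reasonable efforts to obtain bottles, Table 8 collects remaining drug at safety follow-up, and 5.5 asks sites to retrieve drug from patients out of contact. The high values arise only if these steps fail. This stands for men who stop. It does not help at the cutoff for men still on treatment, because final collection follows permanent discontinuation.
- **Visibility.** SAP 5.2.7 reports median, quartiles and range, and SAP 6.5.5 lists derived compliance by patient. In about 20 men a value of 290% would be noticed. This stands for outliers but not for the under-taker who reads as 100%.
- **Following the protocol.** The SAP is applying an explicit protocol rule, and capsule counts always have this weakness. That is fair for masking. It does not excuse counting a supply that the patient has not yet had time to take.

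Four stronger readings are tempting, and the documents do not support them.

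- A reader might add a full unused supply at day 730 and obtain (2920 + 224)/2920 = 107.7%. Dispensing falls on days 701 and 757, and even the ±7-day window puts the latter no earlier than day 750. The ceiling at day 730 is 103.6%. A large excess at the cutoff needs a man with short exposure who has already progressed and is still on drug.
- A reader might infer that any unreturned bottle inflates compliance. An unreturned empty bottle causes no error.
- A reader might infer that values far above 100% mean extra capsules were swallowed. The formula produces them with no dose above plan.
- A reader might infer that the reading of lesion response rests on this table. Cumulative and average daily dose come separately from the dosing page, and no analysis visible in the documents uses compliance. The primary analysis (SAP 6.1) requires NaF-1 and NaF-3 scans, with no compliance threshold.

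**Conclusion.** The rule is wrong as written, and the consequence is minor. Following SAP 6.5.5 literally can yield impossible compliance: up to 290% for a last dose on day 29 and 165% just after week 13 dispensing, falling to 115% at one year and no more than about 108% around two years. It can also report under-dosing as full compliance.

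These are ceilings. They assume on-schedule dispensing, the full daily dose and no capsules returned. The number of patients with unreturned or open supply is not in the documents, so the actual shift in the mean cannot be computed. One patient moves a 20-patient mean by 9.5 points in the day 29 case but by 0.4 points or less around two years. A value above 100% does not by itself put an adherent man in the wrong category; only the under-taker who returns nothing is misclassified. The primary and secondary endpoints are unaffected.

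**What to change.** In SAP 6.5.5:

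1. Compute taken and expected capsules over the same dispensing intervals, using only intervals closed by a later drug-accountability record. Leave out supply, and its days, not yet reconciled at the data cutoff.
2. Keep the Protocol 6.3 assumption for the main table, but report the number of patients with unaccounted supply and flag every value above 100%. Step 1 removes the excess at the cutoff. An early stopper whose closed interval shows nothing returned would still read high, and the flag makes that explicit.
3. Add a supplementary summary restricted to intervals with returned and counted bottles. It should not replace the main table, because dropping unreturned intervals may remove the least adherent patients.

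The counts are already on the Study Drug Accountability page. SAP section 2 lets the SAP modify protocol plans and calls for an amendment only for major changes to the primary endpoint or its analysis, so none appears to be needed. The cost is a little programming and partial compliance data for some patients.

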10.5 Other Analyses

Exposure: The dose and cumulative dose of enzalutamide (mg) will be summarized with descriptive statistics: n, mean, standard deviation, median, and range.

Treatment compliance: Will be measured by the number of capsules taken during the entire study divided by the expected number of capsules, multiplied by 100%.

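### The compliance rate in SAP 6.5.5 is blind to missed doses recorded on the dosing page, because those days are removed from the expected capsule count whatever the reason

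*SAP*

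**What the plan says.** Protocol 10.5 defines compliance as the "number of capsules taken during the entire study divided by the expected number of capsules", expressed as a percentage. It does not define the expected number and mentions no deduction for interruptions. SAP 6.5.5 uses the same ratio and supplies the detail:

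- **Starting count.** With no dose modification, expected capsules are 4 for each day from first to last dose, inclusive.
- **Reductions.** One capsule per day is deducted at 120 mg and two at 80 mg.
- **Interruptions.** "If a dose interruption, then subtract the appropriate number of capsules (4 or 3 or 2"), and this applies to each interrupted day.
- **Definition of interruption.** "A dose interruption will include a missing or a zero dose on the dosing page". No reason or decision-maker is specified.
- **Numerator.** Returned capsules come from the drug accountability page, which is separate from the dosing page. Unreturned capsules count as taken, a rule carried over from Protocol 6.3.

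The rate is summarized as a continuous measure and in two categories split at 80%. The same SAP section also reports treatment duration, cumulative dose, average daily dose over days actually on drug, the number of patients with an interruption, reasons for dose modifications, and a listing.

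**The concern.** Protocol 6.3 gives capsule accountability the purpose of documenting that patients kept to the regimen. A dose the patient skipped is a departure from the regimen, so it should stay in the expected count. The protocol also treats the two situations separately: 6.2.3 tells patients what to do about missed doses, while 6.2.4 speaks of interrupting treatment for toxicity. The SAP puts both under one word and removes both from the denominator.

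The result runs the wrong way. The more carefully a site records skipped doses, the higher the compliance rate; a site that leaves them unrecorded but collects the capsules reports a lower one. Protocol 3.5 interprets lesion change at NaF-3 as response to enzalutamide, so a reader will naturally look to the compliance row for evidence that the drug was taken. With about 20 patients, each patient placed in the wrong category moves that row by 1/20 = 5 percentage points.

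**Working it through.** The documents give no compliance figure to reproduce, so the check applies the SAP formula to assumed patients.

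**Inputs from the documents:** 4 capsules of 40 mg per day (Protocol 6.2.3); the expected-count rules and definition of interruption (SAP 6.5.5); unreturned capsules count as taken (Protocol 6.3).

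**Assumptions:** treatment durations D of 84, 365 and 730 days; capsules dispensed equal to 4D; no dose reductions; shares of days skipped from 10% to 50%.

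**Formula:** compliance = 100 × (dispensed − returned) / (4D − 4 × days recorded as missing or zero).

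**1. Skips recorded, capsules returned.** For D = 365 with 110 days skipped, capsules taken = 4 × (365 − 110) = 1020.
- SAP rule: 1020 / (1460 − 440) = 1020/1020 = 100%.
- Skipped days kept as expected: 1020/1460 = 69.9%.

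The SAP rule gives 100.0% for all three durations and every share skipped, so the below-80% category is never reached.

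**2. Skips recorded, capsules not returned.** For D = 84 with 25 days skipped, the numerator stays at 336 while the denominator falls to 4 × 59 = 236: 336/236 = 142.4%. The same happens if 25 entries are simply blank although the doses were taken.

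**3. Skips not recorded, capsules returned (D = 84).**

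| Days skipped | SAP rate |
|---|---|
| 8 | 304/336 = 90.5% |
| 17 | 268/336 = 79.8% |
| 25 | 236/336 = 70.2% |
| 42 | 168/336 = 50.0% |

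Here the 80% cut works.

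**4. Skips not recorded, capsules not returned.** 336/336 = 100.0%, because of the unreturned-capsule rule alone.

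**5. Mixed recording (D = 84, all capsules returned).**
- 25 days skipped, 12 recorded and 13 not: 236 / (336 − 48) = 236/288 = 81.9%.
- 42 days skipped, 21 recorded and 21 not: 168/252 = 66.7%.

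In general, if a share r of days is recorded as skipped, the unrecorded share with capsules returned must exceed 0.2 × (1 − r) before the rate falls below 80%.

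**6. Other exposure measures.** For 25 recorded skips in 84 days, average daily dose is 160 × 59/59 = 160 mg/day on the SAP denominator, against 160 × 59/84 = 112.4 mg/day over the whole period. Cumulative dose does fall, to 160 × 59 = 9440 mg against 160 × 84 = 13,440 mg, but the SAP forms no ratio of cumulative dose to planned dose.

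**7. Effect of the proposed rule.** Suppose D = 84, with 7 directed interruption days and 20 days skipped by the patient, all recorded and all capsules returned.
- SAP rule: 228/228 = 100%.
- Only the directed days subtracted: 228 / (4 × 77) = 228/308 = 74.0%.

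**The case against.** Measuring adherence against the dose in force, and reporting interruptions separately, is a coherent convention. The SAP introduces its deductions as adjustments for dose changes, and for directed interruptions that is sensible. The unreturned-capsule rule comes from the protocol and is not an error of this SAP section. Compliance defines no analysis set, and no efficacy estimate depends on it. All of this stands. None of it explains why a dose the patient skipped, or an entry left blank, should be deducted as well.

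A reader might also infer that the rate cannot detect non-adherence at all, or that it will sit near 100% for almost everyone. The documents do not support either. Deductions depend on the dosing page and returns on the accountability page, so an unrecorded miss with returned capsules still lowers the rate. How often each pattern will occur depends on how sites complete the dosing page, which neither document describes.

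Nor is compliance the only view of drug intake. Cumulative dose read against duration, the interruption table, the reasons for modification and the listing all keep some signal, and a rate above 100% would be a visible anomaly. These displays show that doses were missed, but they do not correct the rate or the patient's category.

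**Conclusion.** The point holds for missed doses recorded on the dosing page. With capsules returned, any number of such days gives 100%; in the 110-of-365 example the rate would otherwise be 69.9% and the patient would change category. With capsules not returned, the rate can exceed 100%. The durations and shares skipped are assumed, and the number of patients affected cannot be estimated from the documents. The consequence is confined to a descriptive summary in an exploratory single-arm study. The primary endpoint and its confidence interval are unaffected, so the severity is minor.

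**What to change.** In SAP 6.5.5, deduct capsules for interruption days only when the interruption is recorded as directed by the investigator or sponsor. Keep days the patient missed and days with a blank dose entry in the expected count. Where the recorded reason cannot separate the two, also report the rate with no deduction for interruptions, still deducting for prescribed dose reductions.

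This is a short text edit and a small programming change, with no effect on treatment. The SAP already plans to tabulate reasons for dose modifications, but it does not show that a blank entry carries a reason or that the reason categories make this distinction; the fallback covers that case. The cost is that reported compliance will be somewhat lower and the table may need a second row.

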6.2.4 Directions for Dose Modification of Enzalutamide

Patients who experience a grade 3 or higher toxicity that is attributed to enzalutamide and cannot be ameliorated by the use of appropriate medical intervention may interrupt treatment with enzalutamide for 1 week or until the toxicity grade improves to grade 2 or lower severity. Following consultation with the medical monitor, study drug dosing may be restarted at the original dose (160 mg/day) or a reduced dose (80 or 120 mg/day).

If enzalutamide is coadministered with a strong CYP2C8 inhibitor, the dose of enzalutamide should be reduced to 80 mg once daily. If coadministration of the strong CYP2C8 inhibitor is discontinued, the enzalutamide dose should return to the dose used before initiation of the strong CYP2C8 inhibitor.

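### SAP 6.5.5 does not exclude zero from a dose reduction or define the previous dose, so a zero-dose interruption can be counted as a reduction

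*SAP*

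**What the plan says.** SAP 6.5.5, under Dose Interruptions and Reductions, gives two definitions:

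- Interruption: "A dose interruption will include a missing or a zero dose on the dosing page".
- Reduction: "A dose reduction is any dose that is lower than the previous dose".

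The umbrella term allows overlap: "Dose modifications include dose interruptions and/or reductions". The sentence after the reduction definition names the reduced levels: "Dosage of enzalutamide may be reduced to either 120 mg/day, or 80 mg/day". The section then plans three patient counts: any modification (with reasons), "Patients with at least 1 dose interruption will be tabulated" and "Patients with at least 1 dose reduction will be tabulated". It also plans a listing of dose administration, modifications and the derived compliance variables.

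Protocol 6.2.4 describes the sequence that tests these definitions. A patient with a qualifying toxicity may interrupt treatment, after which "study drug dosing may be restarted at the original dose (160 mg/day) or a reduced dose (80 or 120 mg/day").

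**The concern.** The two definitions are not mutually exclusive, although the SAP reports them on separate lines. A dose of 0 mg is numerically below 160 mg, so the record that defines an interruption also satisfies the reduction rule. When treatment resumes at 120 mg, the preceding record is 0 mg, so the restart is a step up and does not satisfy the rule. The rule therefore flags the pause and passes over the actual lowering of the dose.

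The protocol itself foresees interruption followed by restart, so this sequence is not a contrived one. At stake is the count of patients whose dose was lowered, which readers use to judge how well the starting dose was tolerated. In a study of about 20 patients, one misclassified patient visibly moves that percentage.

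**Working it through.** The plan states no figure on this point, so there is nothing to reproduce. The check applies the definitions to short dose sequences. The sequences are illustrations, not trial data.

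**Inputs.** The interruption and reduction definitions and the two reduced levels come from SAP 6.5.5. The restart options of 160, 120 or 80 mg/day come from Protocol 6.2.4. The approximate size of 20 comes from Protocol 10.6 and SAP 5.1.

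**Readings compared.**

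1. Record to record, with a missing dose not comparable to a number.
2. Record to record, with a missing dose ranked below any number.
3. Record to record, with only a step to 120 or 80 mg counted.
4. Each non-zero dose compared with the last previous non-zero dose.

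**Reductions counted per sequence (mg/day).**

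| Sequence | Interruption? | Reading 1 | Reading 2 | Reading 3 | Reading 4 |
|---|---|---|---|---|---|
| 160-120 | no | 1 | 1 | 1 | 1 |
| 160-0-160 | yes | 1 (160 to 0) | 1 (160 to 0) | 0 | 0 |
| 160-0-120 | yes | 1 (160 to 0) | 1 (160 to 0) | 0 | 1 (160 to 120) |
| 160-missing-160 | yes | 0 | 1 (160 to missing) | 0 | 0 |
| 160-missing-120 | yes | 0 | 1 (160 to missing) | 0 | 1 (160 to 120) |
| 160-120-0-120 | yes | 2 (160 to 120, 120 to 0) | 2 (same) | 1 | 1 |
| 160-120-0-80 | yes | 2 (160 to 120, 120 to 0) | 2 (same) | 1 | 2 (160 to 120, 120 to 80) |

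**What the table shows.**

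- 160-0-160: the dose was never lowered, yet readings 1 and 2 put the patient in the table of patients with at least one reduction.
- 160-0-120: readings 1 and 2 count the patient, as they should, but through the step to zero. Reading 3 drops the patient altogether.
- Missing records: the result depends on how a missing value is ranked, and the SAP does not say.
- Direct step-downs (160-120) are classified correctly under every reading.
- Only reading 4 classifies every sequence as the names of the two categories imply.

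**Size.** If k patients have a zero-dose record and no true reduction, and about 20 are treated, the reported percentage is too high by k/20. For k = 1 that is 1/20 = 5 percentage points, and for k = 4 it is 4/20 = 20 points. The documents give no interruption frequency, so k is unknown and may be zero.

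**Outputs that do not move.**

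- The interruption count uses only its own definition.
- The any-modification count is a union, so a record that meets both definitions adds nothing.
- The compliance formula adjusts by days at each dose level and days of interruption, and does not call on the reduction definition.

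**The case against.** The strongest reply is that context makes the intent clear. The next sentence lists only 120 and 80 mg/day as reduced levels, so zero is not one of them. The compliance rules handle reductions and interruptions separately. For an interrupted day they say "then subtract the appropriate number of capsules (4 or 3 or 2"), which carries the patient's current dose level through the zero-dose days (at 40 mg per capsule: 160/40 = 4, 120/40 = 3, 80/40 = 2). On that view the previous dose is naturally the last dose level, not the zero record.

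This shows what was intended, and it stands as such. It does not repair the rule. A programmer who uses the list of reduced levels to exclude zeros, but still compares successive records, arrives at reading 3 and loses the 160-0-120 reduction. SAP 3.4 applies a non-zero qualifier when it fixes the first and last dose dates, so the device was available and is absent here.

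The reply is right to limit the consequences. A reader might infer any of the following, and the documents do not support them:

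- *Every interruption is also a reduction.* An interruption can be a missing dose, which is not lower than 160 mg unless the program ranks it so. The reduction count therefore need not reach the interruption count.
- *All the dose-modification tables are wrong.* Only the table of patients with at least one reduction can be inflated.
- *Patients restarted lower after a zero dose drop out of the reduction table.* Under the literal reading they are still counted, through the step to zero.
- *Reductions are reported with the wrong date.* SAP 6.5.5 plans no date of, or time to, reduction. The misplaced flag affects the listing, which also shows the doses themselves.

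Tolerability is also described by the adverse event tables in SAP 6.6.1, and nothing there ties them to this definition.

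**Conclusion.** The point holds as a minor defect in a descriptive exposure summary. Read as written, the rule counts a patient with a zero-dose interruption and no lowering of dose as having had a reduction. The size is 5 percentage points per such patient, assuming about 20 treated patients and that interruptions are entered as zero-dose records. How many patients this would affect cannot be estimated from the documents.

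For a lower restart after a zero dose, the patient count is right under the literal reading and the flagged record is wrong. The count itself goes wrong only if zeros are excluded without changing the comparison dose. There is no effect on the primary or secondary endpoint or on the sample size.

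**What to change.** Replace the reduction sentence in SAP 6.5.5 with a rule to this effect: a dose reduction is a non-zero dose lower than the most recent previous non-zero dose; a record with a zero or missing dose is an interruption only and is never itself a reduction. Both halves are needed, since excluding zeros alone loses the lower restart.

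The cost is a sentence or two in the SAP, settled before the exposure tables are programmed. It needs no new data. SAP Section 2 ties protocol amendments to major changes in the primary endpoint or its analysis, and this change touches neither. It alters how recorded doses are classified and leaves the dosing instructions as they are.
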